**Table 1 Censoring Rules for Progression-Free Survival**

Situation	End Date	Censored
Documented PD during the study	Date of the first assessment of the series of the tests that determined PD	No
Death during the study before PD	Date of death	No
Discontinued due to PD, but no documented PD	Date of observation of clinical progression (tumor timepoint response assessment CRF page) or date of discontinuation.	No
No baseline assessments	Date of randomization	Yes
Treatment discontinuation for other than PD or death, and no post-baseline tumor assessments	Date of randomization	Yes
Treatment discontinuation for other than PD or death with post-baseline tumor assessments	Date of last tumor assessment	Yes
Death or PD after two or more missed tumor assessments	Date of last tumor assessment before missed tumor assessment	Yes
Subjects still on treatment without PD as of data cut-off	Date of last tumor assessment	Yes
Only NE assessments after CR, PR, SD	Date of last tumor assessment before NE assessment	Yes

Note1: During the study includes Stage 2 treatment phase and follow-up period.

### 9.1.2 Best Overall Response (per eCRF)

Best overall response as assessed by the Investigator (with confirmation required for CR and PR) will be determined by RECIST criteria v1.1 per the eCRF and used in data display and analyses. The responses, listed from best to worst will be: complete response (CR), partial response (PR), stable disease (SD), progressive disease (PD), and not evaluable (NE).

The number and percentage of subjects in each category of best response and best Overall Response Rate (CR + PR) will be summarized for RX-0201 in combination with everolimus, and groups combined. The corresponding 95% confidence intervals will be computed by treatment group using the Clopper-Pearson method for calculating the exact binomial intervals.

### **9.1.3 Time to Response**

Time to response is defined as time from first dose to first PR or CR (that is subsequently confirmed).

The distribution of time to response will be estimated and graphed using Kaplan-Meier method. If applicable, estimates of the 25th percentile, median and 75th percentile and their respective 95% confidence intervals will be provided.

Kaplan-Meier curves for RX-0201 in combination with everolimus will be estimated separately but displayed on one graph as a visual comparison of the survival curves between treatment groups. The log-rank test will be performed to compare the survival curves at the 0.05 significance level.

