9.5.2.3 Time to Event Analyses

The detailed statistical analysis methods for each endpoint will be described in the statistical Analysis Plan (SAP). The Kaplan-Meier method will be applied to the following time to event endpoints:

- Progression-Free Survival: The time from first study dose to the first observation of disease progression (as classified by RECIST ver. 1.1) or death due to any cause.
- Time to response: The time from first study dose to the first observation of a complete or partial tumor response that is subsequently confirmed.
- Duration of response: The time from the first observation of a complete response or partial tumor response (whichever comes first) to the subsequent time of disease progression or death (whichever comes first) will be calculated as the duration of response for each subject.

Kaplan-Meier estimates and 2-sided 95% confidence interval for landmark times by 6-week intervals will be produced for the endpoint of progression-free survival time. Descriptive statistics for the duration and time to response for the responding subjects will be calculated.

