### **7.3.5 Adjustment of Confidence Intervals and p-values**

Any statistical tests that are utilized will be two-sided, with a type 1 error rate of 5%. All confidence intervals will be two-sided, constructed at the 95% confidence level. Any inferential statistical tests conducted in this study will be considered exploratory in nature; therefore, no p-value adjustments for multiplicity analyses will be made.

Data will be summarized using the Safety Analysis Set with respect to enrollment and disposition summaries, demographics and baseline characteristics, concomitant medications, and safety measures. Summary (i.e. descriptive) statistics will include N, mean, standard deviation, median, range (minimum, maximum), values for continuous variables and frequencies, and percentages for categorical variables. Time-to-event analyses will be summarized using Kaplan-Meier survival analysis and graphs. 95% confidence intervals for the estimated median times and percentiles will also be displayed if applicable.

Missing or invalid data will be generally treated as missing, not imputed, unless otherwise stated (see Section 7.4).

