## **9 Efficacy Analyses**

### **9.1 Primary Efficacy Analysis**

Tumor assessment(s) will be performed by the investigator using RECIST Version 1.1 criteria with modifications (Appendix E of the protocol) at the end of every 2 cycles

Subjects first meeting criteria for complete response or partial response at the last on-treatment tumor assessment should have a follow-up tumor assessment at the End of treatment or Early Termination visit providing it is  $\geq 3$  weeks from the previous tumor assessment.

The results will be available before the beginning of the next cycle. Radiographic tumor assessment(s) performed during the screening period will be used to prospectively identify all sites of disease present at the start of treatment. Subjects with symptoms suggestive of disease progression will be evaluated for tumor progression at the time symptoms occur.

The efficacy endpoints analyzed for this study are tumor response (complete response (CR) plus partial response (PR) according to RECIST), progression-free survival (PFS), time to response and response duration (for responders only). Progression-free survival is defined as time from first dose to the earlier of either first documented disease progression or death from any cause. Time to response is defined as time from first dose to first PR or CR (that is subsequently confirmed). Duration of response will be defined as time from first PR or CR (that is subsequently confirmed) to the earlier of either first documented disease progression or death from any cause.

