**13 Listing of Tables, Listings and Figures**

FIGURE NUMBER	FIGURE TITLE	POPULATION FOR ANALYSIS
1	Waterfall Plot (maximum % reduction from baseline in tumor size – target lesions only)	Evaluable for Tumor Response Analysis Set
2	Kaplan-Meier Plot – Progression Free Survival	Evaluable for Tumor Response Analysis Set
3	Kaplan-Meier Plot – Time to Response	Evaluable for Tumor Response Analysis Set
4	Kaplan-Meier Plot – Duration of Respons (if applicable)	Evaluable for Tumor Response Analysis

16 Appendices

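### Time to response is planned as a Kaplan-Meier curve with a log-rank test, but without a rule for non-responders or a consistent population, so the curve can overstate response

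*SAP*

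**What the plan says.** **Method.** SAP 9.1.3 defines time to response as first dose to first confirmed PR or CR. It then states: "The distribution of time to response will be estimated and graphed using Kaplan-Meier method". The 25th percentile, median and 75th percentile with 95% intervals follow where applicable. On groups it says "Kaplan-Meier curves for RX-0201 in combination with everolimus will be estimated separately but displayed on one graph", and then "The log-rank test will be performed to compare the survival curves at the 0.05 significance level".

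**Non-responders.** Neither SAP 9.1.3 nor the definition in SAP 4.3 gives a censoring rule for this endpoint. PFS has one (SAP 4.3, and 9.1.1 with its censoring table), and so does duration of response (SAP 4.3 and 9.1.4). No competing-risk method appears in either document.

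**Population.** Three places in the SAP bear on it:
- SAP 7.2.1 assigns all efficacy endpoints to the Full Analysis Set.
- SAP 9.1 lists "time to response and response duration (for responders only", and the bracket closes there.
- SAP 13 lists "Kaplan-Meier Plot – Time to Response" for the Evaluable for Tumor Response set, which SAP 7.2.5 defines by a measurable lesion at baseline, not by response.

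**Protocol.** Section 9.5.2.3 lists time to response among the endpoints for Kaplan-Meier. It also plans a responders-only summary: "Descriptive statistics for the duration and time to response for the responding subjects will be calculated".

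**Status of tests.** SAP 7.3.5: "Any inferential statistical tests conducted in this study will be considered exploratory in nature".

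**The concern.** Kaplan-Meier treats a censored subject as still able to have the event later. A subject who progresses is not in that position, because protocol 6.9 has subjects with objective progression withdrawn from study treatment. For this endpoint, progression and death are competing events. Censoring them removes subjects from the risk set and credits them with the later response experience of those who remain.

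The curve would then plateau above the response rate reported beside it under SAP 9.1.2. The planned 25th percentile could be printed as reached when fewer than a quarter of subjects responded. Because the rule is not written down, the choice that decides this would fall to the analyst.

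The test is a separate matter. A comparison between groups is announced, but only the combination is named as having a curve.

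**Working it through.** **1. The plan's own figures.** The documents give no figure for time to response. The only precision statements are the 90% interval half-widths for 9-month PFS in protocol 9.3: 0.28 for n = 10 and 0.20 for n = 20. Exact Clopper-Pearson intervals at a proportion of 0.5 give 0.278 and 0.198, so these reproduce, but they do not bear on this point.

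**2. A small worked case (invented data, n = 20, scans every 6 weeks).**

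| Week | At risk | Responses | Progressions |
|---|---|---|---|
| 6 | 20 | 2 | 5 |
| 12 | 13 | 1 | 4 |
| 18 | 8 | 1 | 3 |

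Four subjects are still on study at week 24 without a response.
- Crude response: 4/20 = 20%.
- Non-responders censored at progression: 1 − (18/20)(12/13)(7/8) = 1 − 0.727 = 27.3%.
- Non-responders kept at risk to maximum follow-up: 20%.
- Responders only: 100%, because every subject in the curve has the event.

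**3. Expected size.** Inputs:
- Scan interval of 6 weeks (protocol 7.6): 42/30.4375 = 1.380 months.
- Median PFS of 9 months (combination) and 4.5 months (everolimus alone), both expectations from protocol 9.3. The 4.5-month value serves here as a pessimistic case for the combination.
- True response of 10%, 20% or 30%. This is an assumption; the documents give no response rate.
- Constant hazards, also an assumption.

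Probability of progression or death per interval: q = 1 − exp(−ln 2 × 1.380/median), which is 0.101 for 9 months and 0.191 for 4.5 months.

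The response probability r per scan is chosen so that the true cumulative incidence after K scans equals p: p = r[1 − (1 − r − q)^K]/(r + q). With censoring at progression or death, the curve shows 1 − (1 − r)^K.

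For p = 20%:
- 9 months, K = 4: r = 0.0642, and 1 − 0.9358^4 = 23%.
- 4.5 months, K = 4: r = 0.0750, and 1 − 0.9250^4 = 27%.
- 9 months, K = 8: r = 0.0401, and 1 − 0.9599^8 = 28%.
- 4.5 months, K = 8: r = 0.0550, and 1 − 0.9450^8 = 36%.

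| True response | 24 wk, 9 mo | 24 wk, 4.5 mo | 48 wk, 9 mo | 48 wk, 4.5 mo |
|---|---|---|---|---|
| 10% | 12% | 13% | 14% | 19% |
| 20% | 23% | 27% | 28% | 36% |
| 30% | 35% | 40% | 42% | 53% |

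Simulation of trials with n = 20 agrees with these values to within about 0.6 percentage points. In the same simulations, censoring at maximum follow-up returned the crude proportion and the responders-only curve always reached 100%. Twenty-four weeks corresponds to 8 cycles. The 48-week horizon matters because combination subjects may continue beyond 8 cycles (protocol 3.4.1).

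**4. The log-rank test.** Stage 2 has 3 everolimus-alone and up to 20 combination subjects (protocol 3.3), so the allocation product is (3/23)(20/23) = 0.1134. By Schoenfeld's formula with d events, power is Φ(|ln HR| × √(0.1134 d) − 1.96). With d = 4 responders in total:
- Hazard ratio 2: Φ(0.467 − 1.96) = 7%.
- Hazard ratio 3: Φ(0.740 − 1.96) = 11%.

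For 80% power, d = (1.960 + 0.842)²/(0.1134 × (ln HR)²), which is 145 events for a ratio of 2 and 58 for 3. There are at most 23 subjects.

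**The case against.** Four objections have force.

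- **No censoring rule is stated.** A reader might infer that the plan is bound to overstate response. It is not: if non-responders are carried to maximum follow-up, there is no excess. Censoring at progression, death or last assessment is the likely default by analogy with PFS, but it remains an assumption. What is certain is that the rule is missing.
- **Overstatement and a responders-only curve are rival readings.** They cannot both apply to one analysis. The bracket in SAP 9.1 may cover response duration alone. The figure list is not conclusive either, since it gives essentially the same evaluable-set label to the duration figure, although SAP 9.1.4 confines that analysis to confirmed responders.
- **The protocol also prescribes Kaplan-Meier.** A reader might infer that the SAP departs from the protocol. It does not: protocol 9.5.2.3 plans both the curve and the responder summary. Dropping the curve is the step that would be a change.
- **The test can be computed.** A reader might infer that it cannot be run because only one curve is named. Both groups have subjects, the sentence refers to treatment groups, and the parallel text in SAP 9.1.1 names both. The sound objection is that the comparator is not named in 9.1.3 and that 3 against 20 tells nothing.

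The excess is also small beside the sampling error. At a 9-month median, 20% becomes 23% at 24 weeks, while the exact 95% interval for 4/20 runs from 6% to 44%. That limits the importance of the point. It does not justify a method that errs in one direction under its likeliest reading.

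**Conclusion.** The point holds, conditionally, and is minor. SAP 9.1.3 plans Kaplan-Meier and a log-rank test for time to response without a rule for non-responders and with inconsistent population wording. For a true response of 20%, the permitted readings give 20% (censoring at maximum follow-up), about 23% to 36% (censoring at progression or death, depending on median PFS and horizon) or 100% (responders only). These figures rest on constant hazards, 6-weekly scans, the protocol's expected PFS medians and assumed response rates of 10% to 30%.

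The log-rank test is computable but uninformative. The consequences are contained: the endpoint is secondary, tests are exploratory, and SAP 9.1.2 reports the response rate separately with exact intervals.

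**What to change.** 1. In SAP 9.1.3, report time to response descriptively among confirmed responders, which the protocol also plans.
2. If a curve is kept, use the cumulative incidence of confirmed response in the response-evaluable set, with progression or death before response as competing events. State how subjects who stop for other reasons are censored.
3. Delete the log-rank test from SAP 9.1.3.
4. Align SAP 9.1 and the figure list in SAP 13 with the chosen population, and state the exception to the Full Analysis Set rule in SAP 7.2.1.
5. Record the departure from the protocol's Kaplan-Meier plan in SAP 11, which now lists no changes. Protocol 9.5.1 requires such changes to be described in the SAP.

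The cost is SAP wording and a standard analysis procedure, with no new data. The price is a slightly less favourable curve and one documented change from the protocol.

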### **9.1.4 Duration of Response**

Duration of response (DoR) will be defined as the time from the first documented response (CR or PR) to either the first documented disease progression or death due to any cause whichever is first.

Subjects achieving a CR or PR, who are alive without disease progression or are lost to follow up at the time of analysis, will be censored at the date of last response assessment.

Only subjects who achieve a best response of CR or PR by the confirmed Investigator Assessment of Efficacy will be included in this analysis. The duration of response will be assessed on a subject-by-subject basis and descriptively summarized by treatment group and overall.

Kaplan-Meier curves for RX-0201 in combination with everolimus will be estimated if applicable.

### **9.1.5 Pharmacokinetics**

Pharmacokinetic parameters such as area under the time-concentration curve (AUC), maximum plasma concentration (Cmax), time to first maximum plasma concentration (Tmax), volume of distribution (Vd/F), terminal half-life (t1/2), and total body clearance (CL/F) will be estimated using standard non-compartmental methods and will be derived from blood plasma concentration versus time for RX-0201 for each subject.

RX-0201 concentrations in plasma will be listed by subject and time point. Concentrations by time data may be plotted for each subject. Pharmacokinetic parameters will be listed by subject and descriptively summarized by dose level. RX-0201 concentration time data will be summarized and plotted by dose group.

For the calculation of summary statistics of the concentration values, values that are below the limit of quantitation (BLQ) of 1.00 ng/mL are treated as 0.00 prior to the first quantifiable concentration and as missing thereafter.

## **10 Technical Details**

Statistical Analysis Software (SAS) version 9.4 or later will be used to analyze the data, create summary tables, subject data listings, and graphical representation of the data.

All SAS programs will be validated via independent validation programs per H2O Clinical internal SOPs.

## **11 Summary of Changes to the Protocol**

None.

**13 Listing of Tables, Listings and Figures**

FIGURE NUMBER	FIGURE TITLE	POPULATION FOR ANALYSIS
1	Waterfall Plot (maximum % reduction from baseline in tumor size – target lesions only)	Evaluable for Tumor Response Analysis Set
2	Kaplan-Meier Plot – Progression Free Survival	Evaluable for Tumor Response Analysis Set
3	Kaplan-Meier Plot – Time to Response	Evaluable for Tumor Response Analysis Set
4	Kaplan-Meier Plot – Duration of Respons (if applicable)	Evaluable for Tumor Response Analysis

16 Appendices

Appendix A. Stage 1 Schedule of Assessments

	SCR 	Cycle 1			Cycle n 				EOT or ET Visit	SFU  Visit
		Day			Day					
Procedures and Treatments	-14	1	8	15	1	8	15	18-21		
Informed consent	X									
Medical and medication history	X									
Complete physical examination including weight and height	X									
ECOG performance status	X	X 			X 				X	X
Pregnancy test	X 	X 							X	
Weight and BSA calculation (everolimus/RX-0201 arm only)		X 	X 		X 	X 				
Resting vital signs	X	X 	X 	X 	X 	X 	X 		X	X
Hematology  , chemistry  , and coagulation 	X	X 			X 				X	
Urinalysis 	X	X 			X 				X	
Eligibility confirmation, randomization	X									
Everolimus administration 		X								
Everolimus compliance 			X 	X 	X	X 	X 		X	
RX-0201 infusion (everolimus/RX-0201 arm only)		X			X					
RX-0201 compliance (everolimus/RX-0201 arm only)			X	X		X	X		X 	
Adverse events  and concomitant medication  assessment		X	X 	X 	X	X 	X 		X	X
Pharmacokinetic sampling				X 						
Disease assessment(s)	X 							X 	X 	
Biomarker blood sample		X 						X 	X 	
Archival Tumor Tissue		X 								
Tumor biopsy (optional)		X 								

Abbreviations: SCR = screening, ECOG = Eastern Cooperative Oncology Group, SFU = safety follow up visit; EOT = end of treatment visit; ET = early termination

- 1 Screening procedures will be performed within 14 days of enrollment/ randomization, except baseline tumor assessment, which can be evaluated within 21 days of enrollment/ randomization
- 2 Cycles 2 – 8 will follow the same assessment schedule
- 3 Safety follow-up visit will occur approximately 30 (+ 7) days after the last administration of RX-0201 or everolimus, whichever occurs later
- 4 Assessment can be performed within 3 days before Day 1 of each cycle
- 5 A serum pregnancy test must be negative for all females of childbearing potential
- 6 A urine pregnancy test must be negative for all females of childbearing potential before treatment begins. If a serum pregnancy test was done and determined negative within 72 hours of planned first dose a urine pregnancy test is not needed
- 7 Vital signs can be assessed up to 3 days before Day 1 and will be assessed whenever a PK sample is collected in Cycle 1
- 8 See Appendix C for analytes to be collected. If screening laboratory tests were performed within 72 hours of Cycle 1 Day 1, they do not need to be repeated on Cycle 1 Day 1. Samples to be taken before any RX-0201 or everolimus is administered9 Everolimus will be taken at the clinic on Days 1, 2, 15, and 16 of Cycle 1, and Day 1 of all other cycles
- 10 Subjects will bring all everolimus packaging (empty and full) to the clinic to determine drug compliance
- 11 RX-0201 compliance will be checked at the Early Termination if the subject was receiving RX-0201 at the time of early termination.
- 12 All adverse events attributed to study drug(s) will be assessed until resolution or return to baseline
- 13 Blood will be collected for subjects enrolled in only Stage 1 at the following time points:
  - Immediately prior to Cycle 1 infusion, then at 1 hour ± 5 minutes, 2 hours ± 5 minutes, 3 hours ± 10 minutes, 4 hours ± 10 minutes, 6 hours ± 10 minutes, and 24 hours (± 1 hour) (ie, Day 2) after start of RX-0201 infusion .
  - Immediately prior to the end of Cycle 1 infusion (ie, Day 15), then at 1 hour ± 5 minutes, 2 hours ± 5 minutes, 3 hours ± 10 minutes, 4 hours ± 10 minutes, 6 hours ± 10 minutes, and 24 hours (± 1 hour) (ie, Day 16) after the RX-0201 infusion pump has been turned off
- 14 Disease assessment will occur at the end of every 2 cycles
- 15 Subjects first meeting criteria for complete response or partial response at the last on-treatment tumor assessment should have a follow-up tumor assessment at the End of treatment or Early Termination visit providing it is ≥ 3 weeks from the previous tumor assessment in order to confirm the response based on RECIST ver. 1.1 criteria
- 16 Biomarker blood samples will be collected within 1 day of the disease assessment (approximately at the end of every 2 cycles and at EOT/ET if applicable)
- 17 Tissue blocks or tissue sections from initial diagnosis or upon diagnosis of advanced metastatic disease will be available for submission to the central laboratory within approximately 4 weeks after initiation of study treatment; exceptions require written documentation of why a sample is not available and prior approval by the sponsor before enrollment

**Appendix B. Stage 2 Schedule of Assessments**

	SCR 	Cycle 1			Cycle n 				EOT or ET	SFU 	
		Day			Day				Visit	Visit	
Procedures and Treatments	-14	1	8	15	1	8	15	18-21			
Informed consent	X										
Medical and medication history	X										
Complete physical examination including weight and height	X										
ECOG performance status	X	X 			X 				X	X	
Pregnancy test	X 	X 							X		
Weight and BSA calculation (everolimus/RX-0201 arm only)		X 	X 		X 	X 					
Resting vital signs	X	X 	X 	X 	X 	X 	X 		X	X	
Hematology  , chemistry  , and coagulation 	X	X 			X 				X		
Urinalysis 	X	X 			X 				X		
Eligibility confirmation, randomization	X										
Everolimus administration 		X	→								
Everolimus compliance 			X 	X 	X	X 	X 		X		
RX-0201 infusion (everolimus/RX-0201 arm only)		X	→		X	→					
RX-0201 compliance (everolimus/RX-0201 arm only)			X	X		X	X		X 		
Adverse events  and concomitant medication  assessment		X	X 	X 	X	X 	X 		X	X	
Pharmacokinetic sampling				X 							
Disease assessment(s)	X 							X 	X 		
Biomarker blood sample		X 						X 	X 		
Archival Tumor Tissue		X 									
Tumor biopsy (optional)		X 									

Abbreviations: SCR = screening, ECOG = Eastern Cooperative Oncology Group, SFU = safety follow up visit; EOT = end of treatment visit; ET = early termination

- 1 Screening procedures will be performed within 14 days of enrollment/ randomization, except baseline tumor assessment, which can be evaluated within 21 days of enrollment/ randomization
- 2 Cycles 2 – 8 will follow the same assessment schedule
- 3 Safety follow-up visit will occur approximately 30 (+ 7) days after the last administration of RX-0201 or everolimus, whichever occurs later
- 4 Assessment can be performed within 3 days before Day 1 of each cycle
- 5 A serum pregnancy test must be negative for all females of childbearing potential
- 6 A urine pregnancy test must be negative for all females of childbearing potential before treatment begins. If a serum pregnancy test was done and determined negative within 72 hours of planned first dose a urine pregnancy test is not needed
- 7 See Appendix C for analytes to be collected. If screening laboratory tests were performed within 72 hours of Cycle 1 Day 1, they do not need to be repeated on Cycle 1 Day 1. Samples to be taken before any RX-0201 or everolimus is administered
- 8 Everolimus (10 mg) will be taken at the clinic on Cycle 1 Day 1, and then at home every day thereafter
- 9 Subjects will bring all everolimus packaging (empty and full) to the clinic to determine drug compliance
- 10 RX-0201 compliance will be checked at the Early Termination if the subject was receiving RX-0201 at the time of early termination.
- 11 All adverse events attributed to study drug(s) will be assessed until resolution or return to baseline
- 12 Disease assessment will occur at the end of every 2 cycles
- 13 Subjects first meeting criteria for complete response or partial response at the last on-treatment tumor assessment should have a follow-up tumor assessment at the End of treatment or Early Termination visit providing it is  $\geq 3$  weeks from the previous tumor assessment in order to confirm the response based on RECIST ver. 1.1 criteria
- 14 Biomarker blood samples will be collected within 1 day of the disease assessment (approximately at the end of every 2 cycles and at EOT/ET if applicable)
- 15 Tissue blocks or tissue sections from initial diagnosis or upon diagnosis of advanced metastatic disease will be available for submission to the central laboratory within approximately 4 weeks after initiation of study treatment; exceptions require written documentation of why a sample is not available and prior approval by the sponsor before randomization
